The Remote Health Management team (Propeller Health) utilizes telehealth concepts, including an FDA-approved sensor, mobile apps, predictive analytics, and feedback to help patients and providers better manage asthma.^{11,12} The sensor monitors the use of inhaled medications (ICS and SABA), capturing the date, time, and number of uses. The sensor transmits this information via Bluetooth to a paired smartphone or hub. The location of the event is also securely uploaded to the cloud if the sensor is connected to the Smartphone at the time the sensor is used. Data can be uploaded to the caregiver's smartphone and to the patient's web portal, which their healthcare team will have access to help overall management.¹³

The sensors will be distributed to participants by the study team. We will aim for participants to engage with the study team before going to the clinic or hospital so the device is ready to use at the time of their appointment. This will require the participants to call the research team and the consent being described over the phone to the participants. At their appointment and when the device is given, the participants will sign the consent.

6. Randomization

After recruitment, participants will be stratified by age, sex, and insurance status. They will then be randomly assigned to one of the two study arms.

After recruitment, participants will be stratified by age (4-7 vs 8-17), sex (M vs F), and insurance type (private vs. public), resulting a total of eight strata (stratum1: 4-7, M, Private, stratum2: 4-7, M, Public, stratum3: 4-7, F, Private, etc.). Since this is not a double-blind study and no centralized randomization system will be implemented, one randomization schedule will be generated for each site. Each randomization schedule will contain all eight strata. To ensure balanced treatment allocations within each stratum, 20 randomization blocks will be generated within each stratum. Each block has a block size of 4 with a random permutation of treatments A and B (eg, block 1=AABB, block2=ABBA, etc). Each site's randomization schedule will begin with a distinct randomization sequence number which is different from the subject ID number. For example, site 1's randomization schedule will begin with randomization sequence number 100001, site 2's randomization schedule will begin with randomization sequence number 2000001, etc.

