The site investigator will assign the randomized treatment to a patient in the sequential order, based on the stratum the patient belongs to.

7. Intervention

- a. After enrollment, participants in the Remote Health Management Sensor group will have the full Remote Health Management Sensor Platform (i.e. mobile application, physician access to inhaler use data, etc.). Research staff will review uploaded sensor data on a daily basis. If participants are enrolled into the control group, they will only receive Standard Asthma Education. The Standard Asthma Education follow the NAEPP (National Asthma Education and Prevention Program) guidelines for asthma management. This will include the following list of topics: 1. What is Asthma (Explanation of symptoms); 2. Asthma triggers (what those are and how to avoid them); 3. Using medications (how to use prescribed asthma medications, the difference between controller medications and rescue inhalers, how to appropriately use a spacer, how to appropriately use a mask); and 4. Managing asthma control (purpose of asthma control test and how to complete it, purpose of an asthma action plan and how to read and complete it, how to appropriately use a peak flow meter).

- b. All participants will receive allergen testing, done by their physicians to ascertain their environmental triggers. This will be incorporated into the Remote Health Management software for the intervention group.
- c. If uploaded data reveals elevated SABA use, healthcare team staff will be expected to contact caregivers if needed to ascertain the context of the elevated use and schedule appointments as needed. Information regarding this contact will be documented in the patient's EMR and available to researchers.
- d. The Remote Health Management Platform will send education, based on management plan and identified asthma triggers, to participant in the intervention group.

8. 1 month from start of enrollment

- a. Control Arm- Caregivers will take the ACT, PAMSE, iTRACC survey, and PACQLQ. Caregivers will also be asked about acute exacerbations, ED visits, and hospitalizations as visits to out-of-network healthcare facilities may not be visible in the EMR. This information will be collected via email or phone for both groups utilizing a REDCap survey link for each participant.

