- b. Intervention Arm- Caregivers will take the ACT, PAMSE, intervention survey, and PACQLQ. Caregivers will also be asked about acute exacerbations, ED visits, and hospitalizations as visits to out-of-network healthcare facilities may not be visible in the EMR. This information will be collected via email or phone for both groups utilizing a REDCap survey link for each participant.

12. Final Visit at 12 Months

- a. A second clinic visit will occur one year after enrollment. This visit will aim to coincide with participants' annual asthma clinic visits.
- b. Control Arm- Caregivers will take the ACT, PAMSE, iTRACC survey, and PACQLQ. Caregivers will also be asked about acute exacerbations, ED visits, and hospitalizations as visits to out-of-network healthcare facilities may not be visible in the EMR. This information will be collected via email or phone for both groups utilizing a REDCap survey link for each participant.
- c. Intervention Arm- Caregivers will take the ACT, PAMSE, intervention survey, and PACQLQ. Caregivers will also be asked about acute exacerbations, ED visits, and hospitalizations as visits to out-of-network healthcare facilities may not be visible in the EMR. This information will be collected via email or phone for both groups utilizing a REDCap survey link for each participant.
- d. During this final study visit, a member of the research team will make sure that that the caregivers have completed the all the study surveys via Propeller or via text, email, or telephone.

13. Semi-structured interviews (After Participant Completion of Trial)

- a. From the intervention arm alone, caregivers who responded that they were interested in further contact from the study team on the exit survey will be contacted.
- b. Caregivers will be interviewed about their experience with the intervention (sensor/app) and about how caregiving for their child's asthma is affected by their experiences of family, community, school, and the health care system.
- c. Caregivers will be informed that the in-person, or telephone, interview will be audio-recorded. In-person interviews will be conducted at Northwestern Medical Campus in private, research rooms.
- d. Interviews will last approximately 60 minutes and conducted by research staff.

14. Semi-structured interviews (Health providers at the end of the trial)

- a. Health providers (e.g., nurses and physicians), who were involved in the trial, will be invited to participate in exit interviews

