| Parent-reported values (un-validated) | School days missed due to asthma | 5 times in total (baseline, 3 months, 6 months, 9 months, study completion) |
| Pediatric Caregiver Asthma-related Quality of Life Questionnaire (PACQLQ) | Parent form of how their child's asthma is affecting both their lives and the life of their child | 5 times in total (baseline, 3 months, 6 months, 9 months, study completion) |

Parental Management Outcomes

| Source | Outcome | Time Point |
|-----------------------------------|--|---|
| Parent report (Survey) | Feasibility and acceptability of Platform | 5 times in total (baseline, 3 months, 6 months, 9 months, study completion) |
| Remote Health Management Platform | Frequency of use of the application (synching) | Monthly data pull |

Physician and Clinical Team Outcomes

| Source | Outcome | Time Point |
|-----------------------------------|---|---|
| Remote Health Management Platform | ICS and SABA use | Monthly download |
| Web Portal/Epic | Asthma-related ED visits, hospitalizations, and oral corticosteroid prescriptions/courses | Monthly Epic data pull |
| Clinician Survey | Feasibility and acceptability of the Platform | 1 month into the study, 6 months and study completion |
| Physician Survey | Feasibility and acceptability of the Platform | 1 month and study completion |
| Remote Health Management Platform | Frequency of use of the web portal | Monthly data pull |

Data Analysis:

Primary Outcomes

- *ACT*: Parent-reported test on their child's asthma control
- *Asthma-related hospitalizations*: Data will be obtained from the EMR and parent report.
- *Asthma-related ED visits*: Data will be obtained from the EMR and parent report.
- *Asthma-related oral corticosteroid use*: Prescription/course data will be obtained from the EMR and parent report.

Secondary Outcomes

- *Inhaler Use*: Use data, including frequency of both SABA and ICS inhalers, will be obtained via the sensor throughout the study period.
- *PAMSE*: Parental Asthma Management Self-Efficacy; self-report survey that measures parental self-efficacy for the management and prevention of acute exacerbations of asthma.
- *PACQLQ*: Paediatric Asthma Caregiver's Quality of Life Questionnaire; will assess the impact of their child's asthma on their lives, the lives of their children with asthma, and the family as a whole.

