# AIM 1. Determine factors influencing clinical and psychosocial outcomes.

Clinical and psychological outcomes of interest include the 12-month rate of asthma-related oral corticosteroid use, ED visits, and hospitalizations, as well as change in mean ACT scores (range of 0 to 27) from baseline to end line (12 months). Psychological outcomes of interest include quality of life score (range of 1 to 7), parental self-efficacy score, and the number of school days missed due to asthma. Potential predictors of outcomes include age (4 to 7 years vs. 8 to 17 years), gender (M vs. F), race/ethnicity (non-Hispanic white, non-Hispanic Black, Hispanic, vs. others), insurance status (private/public), and co-morbidities.

Each count variable (asthma-related oral corticosteroid use, ED visits, and hospitalizations) will be analyzed by mixed negative binomial regression analysis adjusting for treatment, all potential predictors, and including maximal random effect structures (i.e., slope and intercept as allowed by the model) of family and clinic. VIFs (variance inflation factors) will be computed for each predictor. Highly correlated predictors (i.e. predictors that can be well-explained by other predictors) will be dropped from the model to avoid multicollinearity issues. Model fit criteria, parameter estimates, and precision of parameter estimates will all be evaluated to select the most parsimonious model.

For each continuous primary outcome variable (i.e., ACT score), change-from-baseline score at each visit will be analyzed using mixed linear regression models, adjusting for treatment, time point, baseline score, all potential predictors, and including random effects (i.e., both slope and intercept) of family and clinic. A treatment by time interaction will be included to evaluate whether the effect of the treatment on the primary outcome varies by time point. VIFs will be investigated for each predictor, and those with high VIFs (VIF>=10) will be dropped from the model to avoid multicollinearity issues. An unstructured covariance (UN) matrix will be assumed. Model fit criteria, parameter estimates, and precision of parameter estimates will also be used to select the most parsimonious model. Model diagnostics will be performed to check model assumptions. All analyses will be performed using statistical analytic software Stata Version 15.1.

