# Missing data and sensitivity analyses:

Missing data will be handled using Multiple Imputations. Sensitivity analyses will be conducted using SAS procedures PROC MI and PROC MIANALYZE. Other sensitivity analyses may be performed if appropriate.

AIM 2. Enhance parental management through improved inhaler use.

After the patient's enrollment visit, parents will be contacted via email or phone at 1, 3, 6, 9, and 12 months to complete a REDCap survey. Descriptive statistics (frequencies and percentages) of each quantitative question will be summarized at each time point and associations between outcomes and demographic predictors will be analyzed by Chi-squared test. Qualitative data will be coded and analyzed by theme analysis.

AIM 3. Improve management by physician and clinical team.

On a biweekly basis, we will collect quantitative data from clinics on the number of time physicians' follow-up with patients and the follow-up outcome. The research team will know exactly how many alerts physicians are receiving, and how physicians are following-up with patients from the Propeller dashboard. The data from the Propeller dashboard will be summarized and associations between outcomes and clinic predictors will be analyzed by Chi-squared test. Clinicians will also be contacted at 1, 3, 6, 9, and 12 months through REDCap surveys to determine if the data is helping them with management and aspects of the platform they like and dislike. Descriptive statistics (frequencies and percentages) from surveys will be summarized at each time point and associations between outcomes and clinic predictors will be analyzed by Chi-squared test.

Qualitative data will be coded and analyzed by theme analysis.

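### Item 12(d) accepts study surveys completed via Propeller, which contradicts the common REDCap route and leaves open an arm-specific mode for the ACT, an unblinded primary outcome

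*Protocol*

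**What the plan says.** Protocol, Study Design and Procedures, item 12 (Final Visit at 12 Months), describes survey collection in two ways.

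- Items 12(b) and 12(c) list the caregiver instruments for the control and intervention arms, with the ACT first in each list. Both end: "This information will be collected via email or phone for both groups utilizing a REDCap survey link for each participant". The same sentence closes each arm's entry at 1, 3, 6 and 9 months (items 8 to 11).
- Item 12(d) has a team member confirm that caregivers have "completed the all the study surveys via Propeller or via text, email, or telephone". It does not separate the arms.

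The SAP, under Aim 2, says that "parents will be contacted via email or phone at 1, 3, 6, 9, and 12 months to complete a REDCap survey". Aim 2 of the protocol says the same. Neither mentions Propeller as a way of answering surveys.

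On access to the app, item 7 (Intervention) says "participants in the Remote Health Management Sensor group will have the full Remote Health Management Sensor Platform", and for the other arm: "If participants are enrolled into the control group, they will only receive Standard Asthma Education".

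The protocol's Data Analysis section lists the ACT first among four primary outcomes and describes it as "Parent-reported test on their child's asthma control". On blinding, item 6 (Randomization) begins one sentence: "Since this is not a double-blind study and no centralized randomization system will be implemented".

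**The concern.** Item 12(d) names the routes that count as completion for all study surveys, and one of them exists in only one arm. A caregiver in the intervention arm could answer the 12-month ACT inside the product under test, which also shows the family its inhaler data and sends educational messages. A control caregiver could not.

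The ACT is subjective and the respondent knows the allocation. If answers depend on the setting in which the questions are asked, or if an in-app route changes who responds, part of the difference between arms would come from how the outcome was collected. The visit concerned is the one that supplies the endpoint, ACT change from baseline to 12 months.

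**Working it through.** **1. The survey routes compared**

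| Place | Route for caregiver surveys | Arms |
|---|---|---|
| Protocol items 8 to 11 and 12(b, c) | REDCap link, by email or phone | Both; 5 visits x 2 arms = 10 entries |
| Protocol Aim 2 | REDCap, after email or phone contact at 1, 3, 6, 9 and 12 months | Not split |
| SAP Aim 2 | As protocol Aim 2 | Not split |
| Protocol item 12(d) | Propeller, text, email or telephone | Not split |

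Item 12(d) is the only one that admits Propeller. It also adds text messaging, but that route is open to both arms.

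**2. Does 12(d) cover the ACT?** It does not name the ACT. It does refer to all study surveys without exception, and 12(b) and 12(c), directly above it, put the ACT among the surveys for that visit. On a plain reading the ACT is covered.

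**3. Do controls have Propeller?** Item 7 gives the platform to the intervention arm and education only to controls. The control-arm timeline has a row for device distribution, which conflicts with item 7. That timeline matches the intervention timeline row for row and looks copied, so it is not evidence that controls receive the app.

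**4. Would the analysis detect or adjust for mode?** The SAP's ACT model is specified as "adjusting for treatment, time point, baseline score, all potential predictors, and including random effects (i.e., both slope and intercept) of family and clinic", plus a treatment-by-time interaction. It has no term for mode of collection, and neither document says that mode is recorded.

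**5. Size.** The plan states no figure on this point. If a share f of intervention surveys is completed in the app and the mode shifts the score by b, the bias in the difference between arms is f x b. The documents supply neither f nor b, and no ACT standard deviation, so what follows is illustration only.

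The sample-size section plans 125 per arm with 20% dropout, so 125 x 0.8 = 100 completers per arm. Assume no true effect, a simple two-sample z-test at two-sided 5%, and b in SD units. The standard error is sqrt(2/100) = 0.141, and the rejection rate is Phi(fb/0.141 - 1.96) + Phi(-fb/0.141 - 1.96).

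| b (SD, assumed) | f (assumed) | f x b | Rejection rate |
|---|---|---|---|
| 0, or any b with f = 0 | any | 0 | 5.0% |
| 0.1 | 0.25 | 0.025 | 5.4% |
| 0.2 | 0.5 | 0.10 | 10.9% |
| 0.2 | 1 | 0.20 | 29.3% |
| 0.3 | 1 | 0.30 | 56.4% |

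The result runs from no effect to a serious one depending wholly on inputs that the documents do not give.

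**The case against.** The strongest reply is that the plan already sets one route. Ten entries say so, two of them for this very visit, and Aim 2 in both documents again names REDCap. Item 12(d) is a completeness check that appears once. The platform's described functions are inhaler logging, location, feedback, education and portal data, and the outcome tables list the ACT and the other questionnaires as sources separate from the platform. No other text says that Propeller can deliver a questionnaire.

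Most of this stands. A reader might infer that the investigators chose to collect the ACT in the app in one arm. The documents do not support that: the weight of the text points to a common REDCap route and to 12(d) as a stray phrase. Nor does anything describe in-app survey prompts or reminders that differ by arm.

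Two things remain. A completeness check that names acceptable routes still tells staff what to accept. The REDCap text is also not watertight for the ACT: in items 8 to 12 the sentence follows the questions on exacerbations, ED visits and hospitalizations and could be read as covering only those, and the questions printed under protocol Aim 2 concern the sensor system. The common route is much the better reading, but it is not stated for the ACT in words that rule out 12(d).

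**Conclusion.** The point holds as an internal inconsistency. Item 12(d) conflicts with items 8 to 12(b, c) and with Aim 2 in the protocol and SAP, and it leaves open an arm-specific mode for an unblinded, caregiver-reported primary outcome at its endpoint visit. This rests on two readings: that all study surveys includes the ACT, and that controls do not have the app, as item 7 says.

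The bias is possible, not demonstrated, and the documents give no basis for its size. A reader might try to express it in ACT points. Assumed app shares of 25% to 50% and assumed mode effects of 0.5 to 1 point would give 0.25 x 0.5 = 0.125 to 0.5 x 1 = 0.5 points. Those inputs are invented, and the range leaves out zero, which is the answer if REDCap is used throughout or if mode has no effect.

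A reader might also infer that no analysis could separate mode from treatment. That is too strong. Text, email and telephone would remain open to both arms, so mode could vary within the intervention arm. If it were recorded, adjusting for mode or excluding app-completed surveys would help in part. The help would be imperfect because families would choose their mode, so prevention is better.

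**What to change.** Delete the Propeller route from item 12(d) and align the rest of that sentence with 12(b, c). State that all caregiver outcome surveys, naming the ACT, are completed in both arms on the same REDCap instrument with the same contact routes (email or phone). Record the mode of each completed survey so that a sensitivity analysis is possible if modes do vary.

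The cost is one protocol sentence and one data field. The downside is slightly less convenience for families who use the app.

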- b. Health providers will be interviewed about their experience using the web portal (Study Aim 3), using the data generated by the sensors, and managing pediatric asthma patients and their interaction with parents
- e. Health providers will be informed that the in-person, or telephone, interview will be audio-recorded. In-person interviews will be conducted at their clinic location in a private office.
- f. Interviews will last approximately 60 minutes and conducted by research staff.

Study Extension

Data analysis will begin 12 months after a participant is enrolled (beginning January 2018.). During the analysis period, we will also determine the feasibility of implementing the intervention more broadly throughout the healthcare system.

Study Subjects:

Eligible participants will be children 4-17 years old with moderate or severe persistent asthma, as diagnosed by their pediatrician, who are primarily seen for their asthma care at one of the participating clinical sites, and who have parents/caregivers willing to participate in this study. Participants will also be required to have received oral corticosteroids in the past year.

Study Enrollment:

Recruitment will occur by a research assistant at all sites. Scheduling of recruitment and participant screening will require the healthcare team to identify potential participants and then the RA either calling or mailing an informational pamphlet to the parents prior to their next appointment. Participants may also be recruited in the clinic by the RA, but will require the RA to follow-up with them via the telephone to properly install and utilize the Remote Health Management Platform. Participants may also be recruited through Lurie Children's Hospital Inpatient service after an asthma exacerbation. Only children who receive their primary care from one of the 5 study clinics will be permitted to be in the study. A member of the research team will work with hospitalists to recruit these individuals.

For the post-trial semi-structured interviews, only those participants who had previously responded that they were interested in further contact by the research team will be recruited. Study staff will contact potential participants for interviews by telephone and only schedule a time if participants remain interested after the interview study has been explained to them.

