- Proventil HFA
- Ventolin HFA
- Xopenex

Supported Controller/Daily Medications:

- Advair HFA
- Advair Diskus
- Asmenex
- Combivent Respimat
- Dulera
- Flovent Diskus
- Flovent HFA
- QVAR
- Serevent Diskus
- Spiriva Respimat
- Striverdi Respimat

Timeline

Pilot: November 2016

- Pilot group of 8-10 families

Phase 1: Enrollment

- December 2016-December 2017
- Collect EMR data from the previous year
- Randomization

Phase 2: Intervention

- December 2016-December 2018
- Intervention Group will have the Remote Health Management device for 1 year
- Standardized Group will receive enhanced, standardized asthma education
- Each group will fill out the following surveys 5x during the study period:
 - ACT
 - PAMSE
 - PACQLQ
 - iTRACC Survey (Control Arm) or Intervention Survey (Intervention Arm)
 - Number of hospitalizations, ED visits, exacerbations
- We will pull information from the EMR to determine oral corticosteroid use

Phase 3: Analysis

- January 2018- December 31, 2018
- All data analyzed
- Preparation and submission of academic abstracts and papers

- Help to prepare for full scale rollout, if applicable
- Semi-structured interviews of subsample of participants
- Semi-structured interviews of health providers in the trial

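### Data analysis is scheduled to open when the earliest participants reach 12 months, and nothing holds the between-arm comparison until the last participant does

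*Protocol*

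**What the plan says.** The protocol's Study Extension section sets the start of analysis: "Data analysis will begin 12 months after a participant is enrolled (beginning January 2018". The trigger is one participant's anniversary, not the last participant's.

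The Timeline at the end of the protocol gives three phases:

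- Phase 1, enrollment: "December 2016-December 2017".
- Phase 2, intervention: "December 2016-December 2018".
- Phase 3, analysis: "January 2018- December 31, 2018". Its items include "All data analyzed" and "Preparation and submission of academic abstracts and papers", followed by rollout preparation and interviews with participants and providers.

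Each child is followed for a year. The section on the final visit says "A second clinic visit will occur one year after enrollment", and the SAP (Aim 1) defines its outcomes over the same horizon: 12-month event rates and "change in mean ACT scores (range of 0 to 27) from baseline to end line (12 months".

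The two Study Timeline task tables (intervention and control) give a second schedule, without calendar years. As extracted, they show recruitment from January to August of Year 1, data analysis from October to July of Year 2, and publications from December of Year 2.

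**The concern.** When the analysis phase spans the last year of follow-up, someone has to decide when the two arms are first compared. These documents leave that decision open. Three features make the gap matter:

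- **Access.** The trial is unblinded, and the outcomes table schedules monthly downloads of ED visits, hospitalizations and oral corticosteroid courses from the medical record.
- **Flexibility.** Under Aim 1, the SAP drops predictors and chooses the simplest adequate model using fit criteria, parameter estimates and their precision. If that is done on partial data, the final model is shaped by early between-arm results, even if no early p-value is ever reported.
- **No error control.** There is no interim plan. Repeated tests at 0.05 raise the chance of a false positive, and a report written before completion would rest on the earlier enrollees.

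**Working it through.** **1. Dates.** Last enrollment (Timeline, Phase 1) is December 2017. Adding 12 months gives a last 12-month visit in December 2018. Phase 3 runs from January to 31 December 2018, so it overlaps the whole final year of follow-up and closes in the month follow-up ends. If the primary comparison waits for the last child, at most about a month remains for collection, cleaning, imputation, modelling and submission.

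**2. Task tables.** The first January enrollee reaches month 12 in January of Year 2, but data analysis starts in October and publications in December, before that. The last August enrollees reach month 12 in August of Year 2, but data analysis ends in July. A column may have shifted in extraction, and pilot families, who also use the device for a year, might explain some early cells. Step 1 does not depend on these tables.

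**3. What the sample size assumes.** Inputs from Sample Size Determination: p1 = 0.545, p2 = 0.75, log(OR) = -0.9181, two-sided alpha 0.05, power 85%, drop-out 20%. Using the Wald test on the log odds ratio:

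n per arm = (z0.975 + z0.85)² × [1/(p1q1) + 1/(p2q2)] / log(OR)²

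= (1.960 + 1.036)² × (4.033 + 5.333) / 0.843 = 99.76

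The total is 2 × 99.76 = 199.5, and 199.5 / 0.80 = 249.4, which rounds up to the stated 250. The figure reproduces as a fixed design with one final test and no allowance for interim looks. The protocol nevertheless names PROC SEQDESIGN, a group-sequential procedure, without giving any number of looks or boundary. The match does not prove that no looks were intended, since a boundary spending very little alpha early would inflate N only slightly. It does mean that none are visible.

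**4. How much data would be complete.** Assumptions not in the documents: uniform accrual over 1 December 2016 to 31 December 2017 (13 months) and no drop-out. With t in months from 1 December 2016, the share with 12-month data is (t - 12)/13.

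| Date | t | Share | Of 250 |
|---|---|---|---|
| 1 Jan 2018 | 13 | 8% | 19 |
| 1 Apr 2018 | 16 | 31% | 77 |
| 1 Jul 2018 | 19 | 54% | 135 |
| 1 Oct 2018 | 22 | 77% | 192 |
| 1 Dec 2018 | 24 | 92% | 231 |
| 31 Dec 2018 | 25 | 100% | 250 |

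With 20% drop-out, spread evenly, the January count is 200 × 1/13, about 15. The share is unchanged.

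**5. Type I error if unadjusted tests were run.** Under the null, take Z(t) = B(t)/√t, where B is Brownian motion and t the information fraction, and reject if |Z| > 1.96 at any look. By simulation, for one outcome:

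| Looks (assumed) | Type I error |
|---|---|
| One final test | 5% |
| 54% and final | 8.2% |
| Two, equally spaced | 8.3% |
| 8% and final | 9.5% |
| Four, equally spaced | 12.5% |
| Five, quarterly (8, 31, 54, 77, 100%) | 15.8% |
| Thirteen, monthly | 21% |

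The documents specify none of these multi-look schedules.

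**The case against.** The strongest reply is that nothing in the documents schedules an early between-arm test. The Study Extension section says only that analysis begins, and adds that feasibility of wider implementation is assessed in the same period. Phase 3 also covers interviews and rollout preparation, and Aims 2 and 3 are largely descriptive or qualitative. All of that can properly start in January 2018, with the primary models run last. This stands. A reader might infer that the protocol plans to test the primary outcomes, or submit papers, from January 2018. It does not say so: submission is one item in a year-long window with no start date of its own.

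Two further points also stand. The type I error figures above 5% depend on looks that we assumed, and the fixed-design sample size points away from planned repeated testing. The completion figures depend on assumed accrual. If the task tables are right and their January is January 2017, almost no child would have 12-month data on 1 January 2018, and the last 12-month visit would fall around August 2018, about four months before Phase 3 closes.

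A last point is partly right. Data-driven model selection is a concern even with one locked analysis, so the calendar does not create it. The calendar does allow the selection to be made on partial results.

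What the reply does not supply is a rule. The benign reading is possible, but neither document requires it, and the stated trigger points to the earliest participants.

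**Conclusion.** The concern holds as a defect in the stated trigger and schedule. Analysis opens in January 2018, follow-up under the Timeline runs to December 2018, and the analysis phase closes in that same month with papers included. The task tables, as extracted, also overlap analysis with follow-up. The text we could read, from which some pages were missing, contains no last-participant rule, lock, interim plan or alpha spending.

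The size is conditional. There is no inflation if one final test is run. If unadjusted early tests were run, type I error would be roughly 8% to 21% under the look schedules assumed here. About 8% of children would have 12-month data on 1 January 2018 under uniform 13-month accrual. Neither range should be read as a property of the trial as planned. The documents support saying that the schedule permits early between-arm analysis and does not control it; they do not support saying that such analysis will happen. The plan should be corrected, because one sentence removes the ambiguity.

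**What to change.** Replace the sentence in the Study Extension section with:

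> The between-arm analysis of outcomes is run once, after the last randomised child's 12-month visit and database lock, with the SAP models fixed beforehand.

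Then:

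- Put the same rule in the SAP, and state whether the use of PROC SEQDESIGN implied interim looks. If looks are wanted, pre-specify their number, timing and alpha spending, and recompute N accordingly.
- In the Timeline, move only the between-arm analysis and the papers that depend on it to after the last 12-month visit. Interviews, feasibility work, descriptive Aim 2 and 3 summaries and pooled data checks may proceed earlier, so the whole of Phase 3 need not move.
- Reconcile the Timeline with the task tables, on both the enrollment window and the start and end of data analysis.

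The cost is a wording change and a later date: primary results and papers come some months later, and that part of the work runs past 31 December 2018 if enrollment continues to December 2017. No extra data or participants are needed unless interim looks are added.
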